8.2 Investigational Drug Assignment and Dispensing Procedures

The investigator or investigator's designee will access the IWRS at Screening to obtain the subject study number. The investigator or the investigator's designee will utilize the IWRS to randomize each qualified subject into the study at Visit 3. During this contact, the investigator or designee will provide the necessary subject-identifying information, including the subject number assigned at screening.

The investigator or investigator's designee will access the IWRS at each dispensing visit to obtain medication identification numbers (Med IDs) for up to two bottles containing 100 tablets

each of either AD-4833 SR 0.8 mg or placebo based on the subject's randomized treatment arm. Subjects will be instructed to take 1 tablet per day, orally, at the same time of day, preferably in the morning, or as directed. Take with or without food. Study drug is to be kept in the container provided until the dose is to be taken. The first dose is to be taken the morning after the randomization visit. The investigator or investigator's designee will utilize the IWRS for Med ID assignment at every subsequent dispensing visit. If sponsor-supplied drug AD-4833 SR 0.8 mg Tablets or placebo is lost or damaged, the site can request a replacement from the IWRS. (Refer to the IWRS manual provided separately.)

The investigator must maintain records of all sponsor-supplied drug delivery to the site. The site will receive a confirmation email from the IWRS providing the Med ID's assigned at each dispensing visit. The site will print, date and initial the email and file in the subject's file as documentation of correct dispensing. The investigator or designee will maintain records of site inventory, dispensation and use by each subject, and return of investigational medicinal product (IMP) to the sponsor or designee. Drug supplies will be counted and reconciled at the site before being returned to the sponsor or designee.

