In general, the baseline value for a variable is defined as the last observation prior to the first dose of double-blind study medication (visit date \leq first dose date), including the screening value, if necessary.

Adverse events that start more than 30 days after the last dose of double-blind study medication (start date – last dose date >30) will be listed, but excluded from the summaries and analyses. For efficacy and other safety data, data that are obtained more than 7 days after the last dose of double-blind study medication (visit date – last dose date > 7) will be listed, but excluded from summaries and analyses. (Note: This efficacy data window only applies to determining which data are included/excluded from the summary statistics and formal statistical analysis tables for a given efficacy endpoint. All events of MCI due to AD (or AD dementia) as determined by the adjudication committee will be included in the time-to-event analyses, without regard to the date of last dose of double-blind study medication.)

If the date of first dose of double-blind study drug collected in the eCRF is missing, then for summary purposes the day after the first dispense date will be used as an estimate for the date of first dose. However, if all dispensed study drug is returned, then the subject is assumed to have not taken any study drug, and the first dose date will not be imputed.

If the date of last double-blind study drug dose collected in the eCRF is missing, then the earliest of the following dates will be used for the last dose date for analysis and summary purposes: date of death, date of last visit (recorded in the eCRF), last double-blind study drug return date, and the last double-blind study drug dispense date (following the last drug return date) + 200 days (ie, the double-blind study drug dispensing interval corresponding to the number of study drug tablets dispensed).

The study window convention will not be applied to the eCRF data listings. The data listings for eCRF data will display the raw data as collected and entered in the eCRF. For efficacy listings, windowed visits will also be shown on the listings.

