9.14.1 Adverse Events

All adverse events will be coded using the latest version of MedDRA. In this dictionary, each verbatim term is coded to a lower level term, and then mapped to a preferred MedDRA term, which is then mapped to an SOC. All adverse events will be included in the data listings but only treatment-emergent adverse events will be included in the summary tables.

A treatment-emergent adverse event (TEAE) is defined as an adverse event with an onset that occurs after receiving study drug (AE start date \geq first dose date) and within 30 days after receiving the last dose of study drug (AE start date – last dose date ≤ 30). A TEAE may also be a pretreatment adverse event or a concurrent medical condition diagnosed prior to the date of first dose of study drug that increases in severity after the start of dosing. Adverse events data with onset occurring more than 30 days after last dose of study drug (AE start date – last dose date > 30) will be listed, but not included in the summary tables. Adverse events with missing onset dates will be summarized regardless of severity and relationship to study medication.

Serious adverse events (SAEs) with onset that occurs after receiving study drug (AE start date \geq first dose date) and within 30 days after receiving the last dose of study drug (AE start date - last dose date ≤ 30) will be summarized.

At the adverse event level, the summary tables will present the number of subjects reporting each of these MedDRA events, ie, the number of subjects reporting one or more events which map to the given MedDRA term.

At the SOC level, the summary tables will present the number of subjects reporting one or more events that map to the given SOC. That is, the number of subjects reported at the SOC level will be less than or equal to the sum of the subject counts across all adverse events within that SOC.

In selected summaries (TEAEs overview, and TEAEs by SOC and preferred term), adverse events will be summarized by the number of events reported in addition to the number and percentage of subjects with events.

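### The rule for a missing last-dose date (SAP 9.1.3) ignores tablets dispensed at the last visit, so later adverse events drop out of the treatment-emergent tables

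*SAP*

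**What the plan says.** For a last-dose date missing from the eCRF, SAP 9.1.3 states: "then the earliest of the following dates will be used for the last dose date for analysis and summary purposes". Three of the candidates are when the subject died, was last seen at a recorded visit, or last handed drug back. The fourth is "the last double-blind study drug dispense date (following the last drug return date) + 200 days". The SAP explains the 200 days as the time that the dispensed tablets should last. Protocol 8.2 agrees: at each dispensing visit, medication numbers are issued "for up to two bottles containing 100 tablets" each, taken at one tablet a day.

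Protocol Appendix A has drug both collected and dispensed at every Month 6 and Month 12 clinic visit. At the EoS/EW visit drug is collected and none is dispensed.

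The last-dose date then decides which events are tabulated. SAP 9.1.3 excludes from the summaries "Adverse events that start more than 30 days after the last dose of double-blind study medication". SAP 9.14.1 counts AEs as treatment-emergent, and summarises SAEs, only if they start on or after first dose "and within 30 days after receiving the last dose of study drug"; later ones are only listed. Deaths are specified as a listing.

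The same date also sets duration of exposure (SAP 9.8), the six-month minimum exposure for the per-protocol set (SAP 9.2), and a 7-day cut-off for efficacy and other safety data (SAP 9.1.3). SAP 9.1.3 exempts adjudicated events of MCI due to AD or AD dementia from that cut-off.

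**The concern.** At a routine clinic visit the old bottles come back and a new supply of up to 200 tablets goes out. A subject who then dies or is lost before the next visit may have no last-dose date and a supply that never returns. The fourth candidate date appears to be written for this subject, because it is defined on a dispensing after the last return. Taking the earliest of the four dates stops it from ever applying. Treatment is deemed to end on the day the new supply began.

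This also conflicts with the SAP's own presumption at the start of treatment. A missing first-dose date is imputed from the first dispensing, and the subject is treated as unexposed only if everything was returned. Unreturned drug is presumed taken at the beginning and ignored at the end.

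At stake is the long-term safety objective. Events reported at the Month 3 and Month 9 calls, or as an SAE between clinic visits, can be classed as off-drug while the subject still holds tablets. A call that confirms dosing does not move the date.

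**Working it through.** **Inputs.** Two bottles of 100 tablets, one tablet a day (Protocol 8.2). Clinic visits every 6 months, nominal days 183, 365 and so on (SAP Table 9.a). AE window of 30 days after last dose (SAP 9.1.3, 9.14.1).

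**1. The plan's own figure.** 2 × 100 / 1 = 200 days. The SAP's 200 days is reproduced.

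**2. Which date wins.** Let R be the last return, D the last dispensing following R, V the last visit and X the date of death. The rule gives min(X, V, R, D + 200).
- Since D ≥ R, D + 200 ≥ R + 200 > R. Once any return exists, the 200-day date cannot be the minimum.
- For a death between visits, X > R, so the date of death cannot be the minimum either.
- What remains is min(V, R).

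An enumeration confirms this. It used ten six-monthly visits, dispensing 0, 7 or 14 days after the return, with and without a call 3 months later, and death on each of days 1 to 182 after the return. The return date was the minimum in all 10,540 cases.

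**3. Share of onset times lost.** With return and dispensing at the same visit:
- Onset uniform over the next 183 days: (183 − 30)/183 = 153/183 = 83.6% fall outside the window.
- Onset on each of the 182 days before the next visit: 152/182 = 83.5%.
- Over the full 200-day supply: 170/200 = 85%.

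**4. Example.** Bottles returned and 200 tablets dispensed on Day 183, call on Day 274, fatal event with onset and death both on Day 330, last-dose date missing.
- SAP rule: min(330, 274, 183, 383) = 183. Onset is 330 − 183 = 147 days later, so it is not tabulated.
- Return date removed, last visit kept (the call counted as a visit): min(330, 274, 383) = 274. Onset is 56 days later and still not tabulated.
- Both removed: min(330, 383) = 330. The event is tabulated.

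Over the enumeration, with onset set to the day of death, the proportions not tabulated are 86.5%, 74.0% and 0% respectively. The last-visit date is therefore as much a cause as the return date.

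**5. Before the first return.** With randomization and dispensing taken as Day 0, a call on Day 91 and death on Day 150, the last visit sets the date: min(150, 91, 200) = 91, and the event is 59 days later. The effect is the same, by a different candidate date.

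**6. Exposure.** Exposure is last dose − first dose + 1, so it loses the whole period from the imputed date to the true last dose, up to one dispensing interval.

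**The case against.** The strongest reply concerns how often the rule applies. The date must be missing after data queries (Protocol 12.1), the end-of-study form required for treated subjects (Protocol 9.3.6), attempts to complete the early-withdrawal procedures and telephone follow-up (Protocol 7.5), and a blinded review of completeness (Protocol 13.1). Leavers who attend an EW visit hand back drug and receive none, so for them the return date is a sensible choice. Subjects lost to contact report few events. Derived-dataset specifications are still to be written and could clarify the fourth date. An earliest-date convention also appears in the compliance rule of SAP 9.8.

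All of this limits the reach, but none of it corrects the rule. A specification that follows the SAP text would program the minimum as written.

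Stronger readings that a reader might infer are not supported:
- **That a fixed share of leavers is affected.** The 12% annual dropout implies 1 − 0.88^5 = 47%, about 1,650 of 3,500 subjects. The documents give no rate of missing last-dose dates, and many leavers will have returned their drug. No count can be derived.
- **That every fatal event between visits is lost.** The window uses AE start date. In the example, a fatal event with onset by Day 213 (183 + 30) would stay in the tables.
- **That the events vanish.** All AEs, SAEs and deaths remain in the listings.
- **That the comparison of arms or the primary result is biased.** The rule is the same in every arm, no differential effect is shown, and adjudicated events are exempt.

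**Conclusion.** The point holds for a defined subset: subjects with a missing last-dose date and a supply dispensed at or after the last return that was never returned. For them two of the four candidate dates, the 200-day supply and a death between visits, cannot be selected once a return is on record. AEs and SAEs starting more than 30 days after the last return or visit are left out of the treatment-emergent tables, and exposure is understated by up to one dispensing interval. The early date can also take a subject below the six-month per-protocol limit and trigger the 7-day data exclusion.

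The figure of about 84% is a share of possible onset times for an affected subject. It assumes uniform onset over 183 days and return and dispensing on the same day. It is not a share of all events in the trial. Calling these events on-drug rests on presuming that unreturned tablets were being taken, as the SAP does for a missing first dose. The algebra is certain; the number of subjects is unknown. This should be corrected as a safety-reporting rule, and it does not threaten the primary analysis.

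**What to change.** Replace the sentence in SAP 9.1.3 with a two-branch rule:

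- **Drug dispensed on or after the last return date, or no return recorded:** impute last dose as the earlier of (a) the date of death for subjects who died, otherwise the date of study discontinuation or last contact, including telephone contact; and (b) last dispense date + 200 days. State that an earlier visit or call does not override the date of death.
- **No drug dispensed on or after the last return:** use the last return date.

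The statement about death is essential. If last contact stayed in the minimum for subjects who died, then with a clinic visit on day 0 and a call on day 91, onsets on days 31–90 and 122–182 would still be excluded: (60 + 61)/182 = 121/182, about 66%. With it, the example above gives min(330, 383) = 330 and the event is tabulated.

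Keep the existing provision that a subject who returned all dispensed drug is treated as having taken none.

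The cost is one SAP sentence and one derivation change before database lock, with no new data collection. The downside is that a few subjects who had already stopped tablets are counted as on drug, which errs toward including safety events and slightly lengthens their exposure.

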9.1.4 Grouping of Centers

Pooling of small sites will be done (if necessary) to form centers for purposes of analysis.

Before unblinding the study, sites that are considered small (<40 subjects) will be pooled with geographically similar sites to minimize artifacts in the statistical analyses from imbalances in subject counts within the sites.

Starting with the smallest center, center(s) with fewer than 40 subjects randomized will be pooled into the nearest center. The pooling will start first within each country; if it is still small, other countries within the same geographical region (for example, US, Europe, Rest of World) will also be considered. The pooled centers within a region which still have fewer than 40 subjects will be kept as they are and will not be pooled with centers in other regions.

The pooling of the centers will be reviewed and approved by the clinical and statistical team for agreement, and will then be used in the appropriate analyses once the database has been locked and unblinded.

Quality issues were detected at site 5055; therefore, data collected exclusively at that site will be excluded for purposes of efficacy analyses.

Because of the smaller number of events available at the time of the efficacy futility analysis, pooling will be done for the efficacy futility analysis using a smaller number of pooled centers, based on country/sovereign state, as shown below.

- US
- UK
- Australia
- Switzerland/Germany

9.2 Major Protocol Violations

All subjects with major protocol violations will be identified prior to unblinding, and will be listed by study center and subject number.

Subjects with the following major protocol violations will be excluded from the per-protocol set (PPS) defined in Section 9.3:

- Age outside of the range 65 to 83, inclusive, at the screening visit.
- CDR Global Score > 0 at Baseline.
- MMSE \leq 24 at the screening visit (after adjusting for education and age as described in Appendix G of the protocol).
- Subject does not have at least one memory test above -1.5 SD of the demographically corrected normative mean at Baseline.
- At Baseline, the subject has a current diagnosis or history of any type of cognitive impairment or dementia, or has a current diagnosis or history of neurological/psychiatric disorder or any other diagnosis that significantly affects cognitive performance (eg, mental retardation, organic mental disorder).
- At Baseline, the subject has a current diagnosis of significant psychiatric illness, per Diagnostic & Statistical Manual of Mental Disorders, 4th Edition - Text Revision (DSM-IV-TR) (or DSM-V when published) (including but not limited to major depressive disorder, anxiety disorders) and is in an acute phase/episode, or the subject has a current diagnosis or history of schizophrenia or bipolar disorder.
- The subject has a glycosylated hemoglobin (HbA1c) >8.0% at the time of baseline or requires treatment with insulin, triple oral antidiabetic therapy or a PPAR- γ agonist. The subject should be on a stable antidiabetic regimen for at least 3 months prior to enrollment.
- The subject has a history of drug abuse (defined as any illicit drug use) or a history of alcohol abuse/dependence within 2 years prior to the Screening Visit.

- Low study drug compliance (<80%).
- Double-blind study medication exposure less than 6 months ($[\text{last dose date} - \text{first dose date} + 1/30.5] < 6$).
- Subject switched treatment during study.
- Randomized treatment different from actual treatment received.
- Incorrect risk stratum assignment used for randomization.
- Subject unblinded prematurely.

The above list may be revised and any additional major protocol violations (eg, related to prohibited concomitant medications) will be identified by the study team prior to final study unblinding.

9.3 Analysis Sets

The safety analysis set will include all subjects who were randomized and received at least 1 dose of double-blind study medication. In safety summaries, subjects will be analyzed according to the treatment they received. In the event that a subject receives more than one treatment, the actual treatment will be defined as the one which is used most frequently. If the two most common treatments are used with equal frequency, then the randomized treatment will be used as the actual treatment.

The full analysis set (FAS) will include all subjects who were randomized, received at least one dose of study drug, and had at least one valid post-baseline value for assessment of primary efficacy. In FAS efficacy summaries, subjects will be analyzed by the treatment to which they were randomized.

The per-protocol analysis set (PPS) will include all FAS subjects who had no major protocol violations. In PPS efficacy summaries, subjects will be analyzed by the treatment to which they were randomized.

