13.1.1 Analysis Sets

All efficacy and safety variables will be analyzed using the full analysis set (FAS). The FAS will consist of all randomized subjects. The per-protocol population will be described in the SAP.

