Following a significant finding for the primary efficacy endpoint, a sequential testing hierarchy will test the rate of cognitive decline endpoint first and then, if significant, proceed to testing the impairment of functional abilities using the functional impairment assessment ADCS ADL-PI As for the primary analysis, these key secondary endpoints will be tested at the $\alpha = 0.01$ level. The analyses for these endpoints will be analysis of covariance (ANCOVA) for change from baseline using mixed models repeated measures (MMRM).

The other secondary endpoints will be analyzed using ANCOVA, logistic regression, survival analyses, or chi-squared tests as appropriate to the data. As for the primary analysis, the secondary endpoints will be tested at the $\alpha = 0.01$ level.

The primary endpoint in this study is event-based and subjects who discontinue from the study prior to having the event will be censored in the primary analysis. However, for completeness, follow-up information will be collected on as many subjects as possible, including the reason for discontinuation. For the continuous variables such as the composite scores, mixed models repeated measures using all available data will be used to evaluate changes over time.

The rules for handling missing items from each of the scales are designed so that as much data as possible can be used in the analyses, yet with reliable information, when calculating total scores.

Missing data may occur in the course of the study or may be due to drop-out. With regard to neuropsychological data collection within the study, missing data can occur under several scenarios. In an interview setting administration of some portions of the test battery may be precluded by tester error or factors attributable to the patient (illness, refusal, or other problems). Neuropsychological technicians will be trained to avoid missing data whenever possible. In the event that an item or a test is missing, technicians will be trained to record the reason for missing data. When tests are scored, the reason for missing data will be coded in a uniform, standardized manner across sites. Test scores will be prorated wherever possible.

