9.9.3.2 Primary efficacy analysis

A similar analysis process as described above for the primary biomarker risk algorithm analysis will be used to compare the placebo- and active-treated non-Hispanic/Latino Caucasian subjects within the high-risk group (ie, using a similar CPH model with covariates of center, gender, and education and an additional covariate of age but using a factor of high-risk treatment group instead of biomarker risk assignment). If this test is significant at the 0.01 level, it can be concluded that active treatment has delayed the development of mild cognitive impairment due to AD.

An exact partial likelihood function will be constructed to fit the Cox proportional hazards (CPH) model to accommodate events with the same times to the event. The robust sandwich estimate for the covariance matrix from the CPH model will be used. The analysis of the primary efficacy comparison will be conducted using the FAS and a CPH model of MCI due to AD events with a factor for treatment and including center, gender, education, and age as covariates.

Parameter estimates, 2-sided 99% CIs, and appropriate p-values for the hazard ratios obtained from the CPH model will be computed to test the null hypothesis of equality of the hazard functions between the high-risk pioglitazone and high-risk placebo treatment groups.

Assessment of the proportional hazards assumption for treatment group will be assessed. Plots of Schoenfeld residuals obtained from the CPH models that fit the primary MCI-to-AD endpoint versus ordered time of events along with a smoothing spline will be used to evaluate the proportional hazards assumption for treatment group. Systematic departures from a horizontal line are indicative of meaningfully non-proportional hazards. Diagnostic checks will be presented in CSR Appendix 16.1.9.

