A subject who does not have an event of MCI due to AD (including AD itself) will be censored for that event at the date of last visit at which a case of MCI due to AD could have been assessed (i.e., the last regularly scheduled visit at which the cognitive battery was assessed or the last unscheduled comprehensive medical follow-up visit at which the CDR was assessed, whichever is later). For subjects who discontinue from the study prior to their first assessment of the cognitive battery or CDR, the date of last contact will be used as the censoring time. At the time of the futility analysis, a subject who has not discontinued from the study and has not had an event of MCI due to AD (or AD) will be censored for that event at the date of the last visit at which a case of MCI due to AD could have been assessed prior to the futility analysis clinical database cut date (ie, the last regularly scheduled visit at which the cognitive battery was assessed or the last unscheduled comprehensive medical follow-up visit at which the CDR was assessed prior to the futility analysis clinical database cut date, whichever is later).

For subjects who die during the trial, the date of death is considered a censoring time for the event of MCI due to AD (rather than as a component of the event of MCI due to AD itself).

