9.17 Changes in the Statistical Analysis Plan from the Protocol Analysis Plan

The study protocol states that academic degrees at baseline will be listed and summarized by treatment group and overall. Information about academic degrees is not collected directly in the eCRF and so won't be presented in the CSR.

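### SAP 9.3 narrows the full analysis set to dosed subjects with a post-baseline value, against the protocol's all-randomised set; roughly 2–6% drop out of the denominators, while the primary Cox result hardly moves

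*SAP*

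**What the plan says.** - Protocol 13.1.1: "The FAS will consist of all randomized subjects". The same section leaves only the per-protocol population to the SAP.
- Protocol 13.1.3, on drop-outs: "subjects who discontinue from the study prior to having the event will be censored in the primary analysis". They are censored, not removed.
- SAP 9.3: an FAS subject is one who was randomised, took study drug at least once, and "had at least one valid post-baseline value for assessment of primary efficacy".
- SAP 9.9.3.2: "The analysis of the primary efficacy comparison will be conducted using the FAS". SAP 9.9.3.1 uses the same set for the biomarker comparison.
- SAP 9.9.4, for subjects who discontinue "prior to their first assessment of the cognitive battery or CDR, the date of last contact will be used as the censoring time".
- SAP 9.17 lists a single departure from the protocol, on academic degrees: "Information about academic degrees is not collected directly in the eCRF". The FAS is not mentioned.
- SAP 5.0 says that changes to principal features of the protocol will go into a protocol amendment. Protocol Amendment 6 still has the all-randomised definition, and its Appendix J shows no change to Section 13.1.1.

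**The concern.** The two documents give different primary populations under one name. The SAP version depends on dosing and on attending an assessment, so it is not an intention-to-treat set. The SAP is also at odds with itself. Section 9.9.4 sets a censoring time for people whom 9.3 has, with few exceptions, already taken out. Section 9.1.3 says that all adjudicated events count regardless of the last dose date, yet under 9.3 an undosed subject who was followed and converted would be excluded.

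The word *valid* adds room for interpretation. SAP 9.9.2 leaves the coding of unreliable or invalid tests to vendor judgement, and 9.1.3 drops efficacy data obtained more than 7 days after the last dose from summaries. Neither section says whether these rules affect FAS membership.

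At stake are the analyses with a subject count in the denominator, and the ability to describe the primary analysis as covering all randomised subjects.

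**Working it through.** **Inputs.** Annual drop-out 12%, 47% over 5 years (protocol 13.3, SAP 8.0). High-risk non-Hispanic/Latino Caucasian subjects: 2,346 required, about 2,940 expected (protocol 6.1). First scheduled efficacy visit at month 6. Battery at the early-withdrawal visit only if more than 3 months after the previous scheduled visit (protocol 9.1.15.2 and Appendix A). Baseline visit about 1 month before randomisation (Appendix A).

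**The plan's own figure.** 1 − 0.88^5 = 47.2%, against 47% stated. The 12% is therefore an annual proportion compounding each year, and early loss by time t is 1 − 0.88^t. Constant loss from day one is an assumption; the documents give no early drop-out figure.

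**Share removed by SAP 9.3.**

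| Who lacks a post-baseline value | Formula | Share | Of 2,346 | Of 2,940 |
|---|---|---|---|---|
| Everyone leaving before month 6 | 1 − 0.88^0.5 | 6.2% | 145 | 182 |
| Only those leaving before month 3 (later leavers do the withdrawal battery) | 1 − 0.88^0.25 | 3.2% | 74 | 92 |
| Only those leaving before month 2 (3-month clock runs from Baseline) | 1 − 0.88^(2/12) | 2.1% | 49 | 62 |

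Subjects never dosed come on top; the documents give no basis for a number.

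**Primary Cox model.** An event is dated at a scheduled visit, so normally not before about month 6. A subject censored earlier is in no risk set and adds nothing to the partial likelihood. In 20 simulated trials (1,173 per arm; exponential hazards from 15% and 9% over 5 years, so a hazard ratio of ln 0.91 / ln 0.85 = 0.580; 12% annual drop-out; events dated 6-monthly), removing the 6.4% on average who left before month 6 changed the log hazard ratio and its z-value by less than 1e-14.

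**Key secondary endpoints.** The repeated-measures models use observed cases (SAP 9.9.6). A subject without post-baseline data supplies no record under either definition.

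**Crude incidence (SAP 9.9.9) and PPV(t) at Years 1–4 (SAP 9.9.10).** The events stay and the denominator shrinks: 1/(1 − 0.021) = 1.02 and 1/(1 − 0.062) = 1.07. Proportions rise by about 2–7% relative.

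**NPV(t).** With the planned 4% low-risk conversion, NPV is about 0.960 if early leavers count as event-free. Removing 6.2%: (0.960 − 0.062)/0.938 = 0.957. It falls slightly.

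**Per-protocol trigger.** SAP 9.9.3.5 runs the per-protocol analysis if more than 5% of the FAS have major violations, and SAP 9.2 counts exposure under 6 months as one. Treating leaving and stopping drug as simultaneous, and looking at this criterion alone:
- All randomised: 6.2%, above 5%.
- SAP set, leavers from month 3 retained: (6.2 − 3.2)/96.8 = 3.1%, below.
- SAP set, leavers from month 2 retained: (6.2 − 2.1)/97.9 = 4.2%, below.
- SAP set, no early leaver retained: 0%, below.

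**Imputation.** The control-based multiple imputation in SAP 9.9.6 fills in values after discontinuation. Under 9.3 the earliest leavers are outside the set.

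**The case against.** The strongest reply is that nothing under alpha control moves. The Cox estimate is unchanged, the other two endpoints in the testing hierarchy use observed cases, and what remains is an additional-variable chi-squared test, descriptive predictive values and a sensitivity analysis. With the primary estimate fixed, a choice between the two sets after unblinding gains little. This stands, and it limits the weight of the point.

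The last-contact rule in 9.9.4 can also be read as a harmless fallback and not as a second population definition. That is fair; the direct contradiction is between SAP 9.3 and protocol 13.1.1.

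A rise in crude incidence or PPV is also not the same as bias. The all-randomised proportion counts never-assessed subjects as event-free, so it is itself low.

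Some stronger readings are tempting but unsupported:
- A reader might take 6% as the loss. It is the upper end, reached only if no one leaving before month 6 completes the withdrawal battery.
- A reader might infer that every proportion is inflated by 1/0.94. For NPV that gives 0.96/0.94 = 1.02, which is impossible. The end-of-study PPV and NPV are already limited to subjects with at least 4 years in the study, so early leavers do not enter them.
- A reader might infer that the exclusion differs by arm. No figure in the documents supports this, the trial is double-blind, and SAP 9.4 reports disposition by treatment group for all randomised subjects, so an imbalance would be visible.

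**Conclusion.** The point holds as an undeclared contradiction about the primary population. The SAP set is conditional on events after randomisation, and the protocol did not leave that definition open. The expected loss is roughly 2–6% of randomised subjects, given constant 12% annual drop-out and depending on the early-withdrawal battery, plus an unquantified number never dosed.

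The consequence is moderate. The documents do not support saying that the primary hazard ratio or the key secondary estimates would be distorted. The affected results are the crude incidence comparison, Year 1–4 PPV(t) (up) and NPV(t) (slightly down), the composition of the imputation set, and possibly the per-protocol trigger. On the exposure criterion alone, the choice of FAS decides whether that trigger is met; other violations could still trip it.

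**What to change.** - In SAP 9.3, define the FAS as all randomised subjects analysed as randomised, with those lacking a post-baseline assessment censored as 9.9.4 already provides.
- Keep the dosed-with-assessment set as a named supportive set, and define *valid*, including how the vendor's missing codes and the 7-day rule bear on it.
- List in 9.17 any exclusion that remains. SAP 9.1.4 leaves data collected only at site 5055 out of the efficacy analyses, so changing 9.3 alone would not give an analysis of all randomised subjects.

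The cost is a change to SAP text before unblinding, with no new data and no loss of power. One side-effect should be stated: with all randomised subjects in the FAS, planned early drop-out alone is likely to pass the 5% threshold, so the per-protocol analysis will probably be run.
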